7.15.2. Method of Assessment

The same method of assessment and the same technique have to be used to characterize each identified and reported lesion at screening, at end of treatment and during follow-up.

Clinically detected lesions will only be considered measurable when they are superficial (e.g., skin nodules and palpable lymph nodes).

Lesions on chest x-ray are acceptable as measurable lesions when they are clearly defined and surrounded by aerated lung. However, CT is preferable.

Conventional CT and MRI should be performed with contiguous cuts of 5 mm or less in slice thickness, if possible [minimum measurable lesion size: long axis \geq 10 mm (CT + MRI) and 2 x slice thickness, if the slice thickness is > 5 mm].

Ultrasound may only be used as a possible alternative to clinical measurements for superficial palpable lymph nodes, subcutaneous lesions, and thyroid nodules.

7.15.3. Baseline documentation of 'target' and 'non-target' lesions

Only subjects with measurable disease at baseline should be enrolled in this study. For evaluation of tumor response, lesions present at screening will be separated into target and non-target lesions according to the following criteria:

Target Lesions:

- All measurable lesions up to a maximum of 2 lesions per organ and 5 lesions in total, representative of all involved organs, should be identified as target lesions and recorded and measured at baseline.
- Target lesions should be selected on the basis of their size (lesions with the longest diameter), be representative of all involved organs, but in addition should be those that lend themselves to reproducible repeated measurements. It may be the case that, on occasion, the largest lesion does not lend itself to reproducible measurement in which circumstance the next largest lesion which can be measured reproducibly should be selected.
- A sum of the diameters (longest for non- nodal lesions, short axis for nodal lesions) for all target lesions will be calculated and reported as the baseline sum diameters. This is the "sum of the longest diameters" (SLD). If lymph nodes are to be included in the sum, then only the short axis is added into the sum. The baseline sum diameters will be used as reference to further characterize any objective tumor regression in the measurable dimension of the disease.

Non-Target Lesions

- All other lesions (or sites of disease) including any measurable lesions over and above the 5 target lesions should be identified as non-target lesions and should also be recorded at baseline. Measurements of these lesions are not required, but the presence, absence, or in rare cases unequivocal progression of each should be noted throughout follow-up.

- It is possible to record multiple non-target lesions involving the same organ as a single item on the eCRF (e.g. “multiple enlarged pelvic lymph nodes” or “multiple liver metastases”)

7.15.4. Evaluation of target lesions

- Measure LD (axial plane) for each target lesion
- Measure short axis for target lymph nodes
- Add these measurements to get the SLD
- If too small to measure, a default value of 5 mm is assigned. If the lesion disappears completely, the measurement is recorded as 0 mm.
- Splitting or coalescent lesions
 - If a target lesion fragments into multiple smaller lesions, the LDs of all fragmented portions are added to the sum
 - If target lesions coalesce, the LD of the resulting coalescent lesion is added to the sum

Table 7-3: Target Lesion Evaluation

Response	Definition
Complete Response (CR)	Disappearance of all target lesions. Any pathological lymph nodes (whether target or non-target) must have reduction in short axis to <10 mm.
Partial Response (PR)	At least a 30% decrease in the sum of diameters of target lesions, taking as reference the baseline sum diameters.
Progressive Disease (PD)	At least a 20% increase in the sum of diameters of target lesions, taking as reference the smallest sum on study (this includes the baseline sum if that is the smallest on study). In addition to the relative increase of 20%, the sum must also demonstrate an absolute increase of at least 5 mm. (Note: the appearance of one or more new lesions is also considered progression).
Stable Disease (SD)	Neither sufficient shrinkage to qualify for PR nor sufficient increase to qualify for PD, taking as reference the smallest sum diameters while on study.

7.15.5. Evaluation of non-target lesions

Table 7-4: Non-Target Lesion Evaluation

Response	Definition
Complete Response (CR)	Disappearance of all non-target lesions and normalization of tumor marker level. All lymph nodes must be non-pathological in size (<10mm short axis).
Non-CR/Non-PD	Persistence of one or more non-target lesion(s) and/or maintenance of tumor marker level above the normal limits.
Progressive Disease (PD)	
Appearance of one or more new lesions and/or unequivocal progression of existing non-target lesions. Unequivocal progression should not normally trump target lesion status. It must be representative of overall disease status change, not a single lesion increase.
 
Although a clear progression of “non-target” lesions only is exceptional, the opinion of the treating physician should prevail in such circumstances, and the progression status should be confirmed at a later time by the review panel (or Principal Investigator).

7.15.6. Evaluation of Best Overall Response

The best overall response is the best response recorded from start of treatment until disease progression/recurrence (taking as reference for progressive disease the smallest measurements recorded since the start of treatment). The patient's best response assignment will depend on the achievement of both measurement and confirmation criteria. Responses will be assessed using CT scans or magnetic resonance imaging according to standard RECIST v1.1 criteria in order to assess disease progression. These criteria will also allow for patients who experience an initial disease flare, and as some patients who will have a delayed response may experience an initial disease flare, these patients will be allowed to continue receiving study treatment beyond progression.

The following table provides overall responses for all possible combinations of tumor responses in target and non-target lesions with or without the appearance of new lesions:

Table 7-5: Time point response: subjects with target (\pm non-target) disease

Target lesions	Non-target lesions	New lesions	Overall response
CR	CR	No	CR
CR	Non-CR/non-PD	No	PR
CR	Not evaluated	No	PR
PR	Non-PD or not all evaluated	No	PR
SD	Non-PD or not all evaluated	No	SD
Not all evaluated	Non-PD	No	NE
PD	Any	Yes or No	PD
Any	PD	Yes or No	PD
Any	Any	Yes	PD

CR = complete response, PR = partial response, SD = stable disease, PD = progressive disease, and NE = inevaluable.

Note: To be assigned a status of PR or CR, changes in tumor measurements must be confirmed by repeat assessments that should be performed 6 weeks after the criteria for response are first met. In the case of SD, measurements must have met the SD criteria at least once after study entry at a minimum interval of 6 weeks.

7.15.7. Duration of Response

Duration of overall response: The duration of overall response is measured from the time measurement criteria are met for CR or PR (whichever is first recorded) until the first date that recurrent or progressive disease is objectively documented (taking as reference for progressive disease the smallest measurements recorded since the treatment started).

The duration of overall CR is measured from the time measurement criteria are first met category when no lesions can be measured is not advised for CR until the first date that progressive disease is objectively documented.

Duration of stable disease: Stable disease is measured from the start of the treatment until the criteria for progression are met, taking as reference the smallest measurements recorded since the treatment started, including the baseline measurements.

7.16 SURVIVAL STATUS

Subjects will be followed up by clinic visits or phone call or another method of contact, for survival status every 3 months (± 1 month) for 2 years after treatment discontinuation or until death, whichever occurs first.

7.17 STANDARD OF CARE

The standard of care should be administered as per the dosing schedule included on the package insert.

8 STATISTICAL ANALYSIS

This section presents general information about statistical considerations and concepts and a brief discussion on analysis methodology, as well as some data conventions. Detailed descriptions of the statistical analysis methods and data conventions that will be used in this study will be in a separate document; i.e., the Statistical Analysis Plan (SAP).

8.1 TREATMENT GROUPS

- 525 mg leronlimab (PRO 140)

8.2 SAMPLE SIZE DETERMINATION AND RATIONALE

Up to 30 subjects will be enrolled in this study. The sample size for is based on clinical judgment. No statistical power calculation is used to establish the sample size.

8.3 RANDOMIZATION AND STRATIFICATION

Not applicable.

8.4 BLINDING

Not applicable.

8.5 INTERIM ANALYSIS

No Interim Analysis (IA) will be performed for efficacy.

8.6 STATISTICAL CONSIDERATIONS

All collected study data will be presented in subject data listings. Statistical analyses will be performed using SAS[®] for Windows, version 9.4 or later. Descriptive statistics (n, mean, standard deviation, median, minimum and maximum) will be presented by treatment group for continuous variables. Frequencies and percentages will be presented by treatment group for categorical variables.

8.6.1. Analysis Populations

8.6.1.1 Evaluable Population

The **Evaluable population** is defined as the set of subjects who have received at least one dose of leronlimab (PRO 140) and have measurable disease at baseline. This population will be used for the analysis of efficacy parameters or measurements

8.6.1.2 Per Protocol Population

The **Per Protocol (PP) population** is defined as the set of subjects who meet the Evaluable Population requirements and were not associated with any major protocol violations. This population will be identified before the database lock.

The PP analysis of primary and secondary endpoints will be considered supportive

8.6.1.3 Safety Population

The **Safety Population** will include all subjects who have received one dose of leronlimab (PRO 140). This population will be used for the analysis of safety parameters.

8.6.2. Covariates

For efficacy analyses, the baseline values will be used as covariates in the analysis models. Other important prognostic factors will be specified in the SAP for the study.

8.6.3. Missing Data

All data will be used as observed, and no imputations will be made for any missing data point for early phase study.

8.7 ANALYSIS METHODS

A SAP will be developed and approved before the database is locked. The SAP will present the detailed statistical methodology to be used in analyzing the data from this trial.

8.7.1. Subject Disposition

The disposition of all subjects who sign an ICF will be provided. The numbers of subjects screened, enrolled, completed, and discontinued during the study, as well as the reasons for all post-enrollment discontinuations will be listed and/or summarized by treatment group. Disposition and reason for study discontinuation will also be provided as a by-subject listing.

8.7.2. Demographic and Baseline Disease Characteristics

Demographics and baseline disease characteristics including medical history, prior and concomitant medications/therapies will be listed and/or summarized by treatment group using appropriate descriptive statistics.

8.7.3. Study Analyses

Safety Outcome Measures:

The safety outcome measures in this study are:

- The number, frequency, and severity of adverse events (AEs) collected from the time of first treatment until 12 weeks after study treatment completion to evaluate safety of leronlimab (PRO 140) in subjects with CCR5+ locally advanced or metastatic solid tumors.

Note: Adverse events will follow National Cancer Institute Common Terminology Criteria for Adverse Events (CTCAE) version 5.0

- Laboratory data changes from baseline to subsequent scheduled visits
- Changes in physical examinations from baseline to subsequent scheduled visits
- Changes in vital signs from baseline to subsequent scheduled visits.
- Changes in Eastern Cooperative Oncology Group (ECOG) performance status from baseline to subsequent scheduled visits.
- Changes of electrocardiogram (ECG) results from baseline to subsequent scheduled visits

Efficacy Outcome Measures:

The efficacy outcome measures in this study are:

- Progression free survival (PFS) defined as time in months from the date of first study treatment to the date of disease progression or death from any cause, whichever comes first.

Note: All patients who receive at least one dose of leronlimab (PRO 140) will be included in the primary analyses of PFS. The Response Evaluation Criteria in Solid Tumors (RECIST v1.1) criteria will be used for objective tumor response assessment (when disease is measurable and non- measurable);

The time in months from start of treatment to progression or death will be measured for all patients who receive at least one dose of study drug. Patients will be followed up to 2 years after completion of treatment.

- Overall response rate (ORR, defined as Complete Response (CR) + Partial Response (PR)), and clinical benefit rate (CBR, defined as CR + PR + Stable Disease (SD)) in subjects with CCR5+ locally advanced or metastatic solid tumors treated with leronlimab (PRO 140).

Note: Overall response rate is defined as the proportion of patients who achieve an overall response of complete response or partial response in the total number of evaluable patients, assessed by RECIST v1.1. Clinical benefit rate is defined as the proportion of patients who achieve an overall response of complete response or partial response or stable disease in the total number of evaluable patients, assessed by RECIST v1.1.

Imaging scans to be done approximately every 3 months or according to institution's standard practice.

- Time to new metastases (TTNM);

Note: Recorded time from baseline metastatic disease (at time of enrollment) to the time of development of new metastasis in different site. New metastases in same site will be also recorded.

- The change from baseline in circulating tumor cells (CTC) level in the peripheral blood.

Note: Reported unit of measure will be the number of CTCs/milliliter. CTCs enumeration will be performed at baseline and at the time of response assessment. Fraction of baseline positive and change from ≥ 5 CTCs will be recorded and reported.

- Overall survival defined as time in months from the date of first study treatment to the date of death;

Note: Patients will be followed from the start of treatment until 2 years post-treatment or death, whichever occurs first, and average survival time will be measured.

Exploratory Outcome (Endpoints) Measures:

- Measure immune biomarkers in CTCs, metastatic tissue and immune cells such as CAML and correlate with therapeutic benefit (PFS); and
- Assess changes in CTCs and CAML after treatment and perform correlative analysis of CCR5 expression.

PFS will be calculated using Kaplan-Meier curves and the median PFS will be read from this curve. Response rates (overall response rate, clinical benefit rate) will be calculated using proportions and 95% confidence intervals. Time to new metastases and overall survival will also be analyzed using Kaplan-Meier curves. Exploratory serial blood markers will be related to PFS using Cox regression, and to response using logistic regression.

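### For a two-level marker and few responders, the planned logistic regression of response on blood markers may have no finite odds ratio, and no fallback is named

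*Protocol*

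**What the plan says.** Protocol 8.7.3 (repeated in the synopsis) gives one sentence on the method: "Exploratory serial blood markers will be related to PFS using Cox regression, and to response using logistic regression". It does not say how a marker is coded, which serial value is used, how many terms are fitted, or what happens if the model does not converge or nobody responds.

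On size, Protocol 8.2 says "Up to 30 subjects will be enrolled in this study" and "No statistical power calculation is used to establish the sample size". No expected response rate appears in either document.

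Two definitions could supply the outcome. ORR counts patients with "complete response or partial response in the total number of evaluable patients, assessed by RECIST v1.1". The other is "clinical benefit rate (CBR, defined as CR + PR + Stable Disease (SD". The regression sentence does not choose between them.

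The CTC marker is described in two ways in the same section. As a quantity: "Reported unit of measure will be the number of CTCs/milliliter". Against a cut: "Fraction of baseline positive and change from ≥ 5 CTCs will be recorded and reported".

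SAP 8.4.1 plans descriptive summaries of the immune biomarkers and contains no logistic model. SAP 5 rules out formal hypothesis testing. SAP 12 describes the document as a first draft.

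**The concern.** Maximum-likelihood logistic regression on a two-level marker has a finite slope only if all four cells of the marker-by-response table are occupied. If every responder falls on one side of the marker, the fitted log odds ratio runs off towards infinity. Software then stops at an arbitrary iteration and prints a very large estimate with a huge standard error, or gives a convergence warning. With at most 30 subjects, a handful of responders makes an empty cell likely by chance alone.

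Low response is plausible but not established. Protocol 3.3.1 admits patients who have progressed on standard therapy, cannot receive it or have none. A dichotomised CTC count is also a foreseeable model term, because the protocol reports the cut at 5 and Protocol 1.2.2 presents that cut as prognostic.

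What is at stake is the correlative part of the secondary objective, which is meant to inform treatment selection in later validation studies. An unusable odds ratio would contribute nothing to it, and changing the method after seeing the table would be a data-driven choice.

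**Working it through.** The plan has no power, precision or response-rate figure to reproduce. Protocol 8.2 says only "The sample size for is based on clinical judgment".

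**Inputs.** n = 30 is the enrolment cap in Protocol 8.2. Response rates of 5% to 30% and marker splits of 15 or 6 positive out of 30 are assumptions, since the documents give neither.

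**Two-level marker, given r responders, no association.** With m marker-positive subjects, the number of responders among them is hypergeometric. The chance of no finite odds ratio is the probability that any cell is zero. For r = 3 and m = 15 it is 2 × C(15,3)/C(30,3) = 2 × 455/4060 = 22%.

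| Responders r | m = 15 | m = 6 |
|---|---|---|
| 1 | 100% | 100% |
| 2 | 48% | 67% |
| 3 | 22% | 50% |
| 4 | 10% | 39% |
| 6 | 2% | 23% |

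For an evenly split marker the problem has largely gone above four responders. For a rarer marker it lasts longer.

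**Averaged over the number of responders.** The values above are weighted by r ~ Binomial(30, p), with r = 0 counted as no estimate. At p = 10% and m = 15, taking r = 0 to 6 in turn:

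0.042 × 1 + 0.141 × 1 + 0.228 × 0.483 + 0.236 × 0.224 + 0.177 × 0.100 + 0.102 × 0.042 + 0.047 × 0.017 ≈ 0.37.

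Higher r adds almost nothing.

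| Assumed response rate | m = 15 | m = 6 | One continuous marker |
|---|---|---|---|
| 5% | 71% | 81% | 24% |
| 10% | 37% | 57% | 5.3% |
| 15% | 17% | 39% | 1.1% |
| 20% | 7% | 27% | 0.2% |
| 30% | 1% | 12% | 0.01% |

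**Single continuous marker, no association, no ties.** Separation requires the r responders to hold the r highest or r lowest values, with probability 2/C(30, r). This is 6.7% at r = 1, 2/435 = 0.46% at r = 2 and 2/4060 = 0.05% at r = 3. Most of the last column in the table is therefore the chance of zero responders: 21%, 4.2%, 0.8% and 0.1% at rates of 5%, 10%, 15% and 20%. If responders and non-responders differ by 1.5 SD, simulation gives about 14%, 6% and 3% at r = 2, 3 and 4. A count with many tied zeros would be less favourable than the no-ties formula. The documents give no CTC distribution from which to say by how much.

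**Two-level marker that does predict response.** Here the marker status of each subject is random. With a true odds ratio of 4 and a 10% response rate, the chance of no finite estimate rises from 39% to 56% at 50% prevalence. It falls from 59% to 40% at 20% prevalence. A real association therefore does not always make matters worse.

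**What penalisation does.** Take 3 responders among 15 marker-positive subjects and 0 among 15 marker-negative. Maximum likelihood gives a log odds ratio of 7.8 (SE 15.6) at iteration 8 and 24.8 (SE about 76,700) at iteration 25. For this table Firth's penalty amounts to adding 0.5 to each cell: OR = (3.5 × 15.5)/(12.5 × 0.5) = 8.68. The fitted probabilities are 3.5/16 = 0.219 and 0.5/16 = 0.031. The variance is 1/(15 × 0.219 × 0.781) + 1/(15 × 0.031 × 0.969) ≈ 0.39 + 2.20 = 2.59, so SE = 1.61. The Wald 95% interval is exp(2.16 ± 1.96 × 1.61), about 0.37 to 204. The estimate is finite and says plainly how little is known.

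**The case against.** A reader might infer that the planned correlative analysis generally breaks down at this sample size, even for any single baseline marker. The documents do not support that. The regression sentence dichotomises nothing, the stated CTC unit is a count per millilitre, and the cut at 5 is something to be recorded and reported rather than a declared model term. For a continuous marker the failure is rare once two subjects respond, and with no responders Firth cannot estimate an association either.

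A reader might also take response to mean CR + PR at a low rate. That too is an assumption. If CBR is meant, or the rate is 30% or more, the chance drops to about 1% for an evenly split marker, although about 12% remains when only 6 of 30 are positive.

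Nor does the protocol prescribe maximum likelihood in so many words. Firth and exact methods are forms of logistic regression, and Protocol 8 and 8.7 leave detailed methods to the SAP. That stands in part: unqualified, the term is normally read and run as maximum likelihood, and the SAP supplies no alternative because it omits the model.

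Finally, the analysis is exploratory, no formal testing is planned, an empty cell would be visible in a table of 30 subjects, and a Firth interval of 0.37 to 204 informs little. All of this is right. It limits the importance of the point, but naming a workable estimator in advance remains a nearly free improvement.

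**Conclusion.** The point holds conditionally. It needs three things together: a marker entered as two levels, about four or fewer responders (somewhat more if marker-positive subjects are few), and maximum-likelihood fitting. Under no association and n = 30, the headline range is then 37% to 57% at an assumed 10% response rate, falling to 1% to 12% at 30%. These figures average over the number of responders at each rate. The rates and marker splits are assumptions, and the outcome definition is left open by the protocol. For a single continuous marker without ties, two or more responders and no association, the risk is under 0.5%. Severity is low: a minor improvement to an exploratory analysis, with no bearing on the main efficacy results.

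**What to change.** In Protocol 8.7.3 (and the matching synopsis sentence), change 'logistic regression' to 'Firth-penalised logistic regression, one marker per model, with profile-likelihood 95% intervals'. Add that CTC is entered as a count where possible, and that marker values only are reported if there are no responders. The same sentence should say whether response means ORR or CBR, since that largely decides whether sparse data arise.

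SAP 8.4.1 has no logistic model to amend. If the model is restored there, it should be restored in this form.

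The cost is a few words of text and one option in the planned SAS software. The statistical downside is slight shrinkage of estimates towards no effect. The change makes estimates finite when there is at least one responder; it does not make them precise, and the report should expect very wide intervals.

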5. PRIMARY HYPOTHESIS TO BE TESTED

There is no formal hypothesis testing for this study as the study is a Phase I/Phase II evaluation and is not intended to be hypothesis generating. The study is not powered to reliably yield statistically significant conclusions.

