7.7 Multiple Comparisons and Multiplicity

There will be no adjustment for multiple testing or multiplicity for this phase II trial. For all effectiveness endpoints, inference will be based on type I error rate of 0.05.

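### Neither document relates the blood markers to the continuous change in target-lesion size: the protocol uses logistic regression on an undefined response, and the SAP gives only descriptive summaries

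*Protocol*

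**What the plan says.** **The marker models.** Protocol 8.7.3, repeated in the Synopsis, states: "Exploratory serial blood markers will be related to PFS using Cox regression, and to response using logistic regression". The same section defines two response rates. For the first, "Overall response rate is defined as the proportion of patients who achieve an overall response of complete response or partial response"; the second, CBR, adds stable disease. The regression sentence does not say which one it uses. The marker endpoint that the protocol and SAP 2.7.3 actually name is correlation with PFS.

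**The measurement behind response.** In Table 7-3 (Protocol 7.15.4), partial response on target lesions is "At least a 30% decrease in the sum of diameters of target lesions, taking as reference the baseline sum diameters". Protocol 7.15.3 says of the baseline value: "The baseline sum diameters will be used as reference to further characterize any objective tumor regression in the measurable dimension of the disease". Measurable disease is required for entry (inclusion criterion 4), and Protocol 7.15.4 has the sum recalculated when target lesions are evaluated.

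**The SAP.** Section 8.4 contains no Cox or logistic model. It offers descriptive summaries of the biomarkers and an unspecified correlative analysis of CCR5 expression. Section 8.1.3 puts tumour imaging in a by-subject listing. Section 5 says "There is no formal hypothesis testing for this study", while section 7.7 says "For all effectiveness endpoints, inference will be based on type I error rate of 0.05".

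**Sample size.** Protocol 8.2 states "Up to 30 subjects will be enrolled in this study" and "No statistical power calculation is used to establish the sample size".

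**The concern.** One secondary objective is correlative work to guide treatment selection in later studies. If response means CR or PR, the logistic outcome is largely a cut of a continuous measurement at a 30% decrease. A subject whose lesions shrink by 29% is then coded the same as one whose lesions grow. RECIST categories are needed to report ORR and CBR, but nothing in either document requires the cut for a marker correlative. With few subjects and possibly very few responders, the yes/no analysis has a weak chance of showing a real association and gives a wide interval for it. The data for a more efficient analysis are already being collected.

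**Working it through.** The plan gives no power, effect size, marker-tumour correlation or expected response rate, so there is no figure of its own to reproduce. The check is a simulation under stated assumptions.

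**Inputs from the documents.** N = 30 at most (Protocol 8.2); type I error 0.05 (SAP 7.7), taken as two-sided because the side is not stated; the cut between responders and others (Table 7-3).

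**Assumed inputs.** One marker value per subject; marker and percent change bivariate normal with correlation ρ; response is the best 10, 20 or 30% of the change distribution.

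**1. Expected responders.** At a 10% response rate, 30 × 0.10 = 3 are expected. P(none) = 0.9^30 = 4%, and P(2 or fewer) = Σ C(30,k) 0.1^k 0.9^(30−k) for k = 0 to 2 = 41%. At 5%, 1.5 are expected, P(none) = 21% and P(2 or fewer) = 81%.

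**2. Power at N = 30.** The Spearman column shows the range over repeated runs.

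| ρ | Spearman on percent change | Logistic likelihood-ratio test, response 10 / 20 / 30% |
|---|---|---|
| 0.4 | 54–57% | 27 / 35 / 41% |
| 0.5 | 75–79% | 40 / 53 / 60% |
| 0.6 | 92–93% | 52 / 69 / 78% |

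Smallest loss: 54 − 41 = 13 points. Largest loss: 93 − 52 = 41 points. With no association, the likelihood-ratio test rejects in about 6 to 8% of trials and Spearman in about 4 to 6%, so the comparison does not handicap the logistic model. A rerun with 10,000 trials per cell agreed within one or two points.

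**3. Wider inputs.** Over ρ 0.3 to 0.7 and response 5 to 50%, with a Pearson test as the continuous comparator (slightly stronger than Spearman under normality), the loss runs from 99 − 95 = 4 points (ρ 0.7, 50% response) to 95 − 36 = 59 points (ρ 0.6, 5% response).

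**4. Other readings of response.**
- CBR near 50%: 4 to 17 points over ρ 0.3 to 0.7, with the same Pearson comparator.
- Ordinal logistic on CR/PR, SD, PD: power 51–53 / 70–72 / 88–90% at ρ 0.4 / 0.5 / 0.6, against Spearman 55 / 77 / 93%, a loss of about 2 to 7 points.

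**5. Subjects without a post-baseline scan.** Suppose 6 of 30 are unscanned, with ρ = 0.5.
- Lost at random and dropped (n = 24): Spearman 64–66%. Against the logistic 40 to 60% with all 30 subjects kept, the gain is 64 − 60 = 4 to 66 − 40 = 26 points.
- The 6 worst subjects unscanned and dropped: Spearman 45%, below the logistic test at 20 and 30% response (53 and 60%).
- The 6 worst ranked at the worst end (largest increase): 76–78%.
- The 6 worst given the lowest value of percent change: 2%. On this scale the lowest value is the greatest shrinkage, so the direction of the rule has to be written out.

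**The case against.** The strongest case against is that this is exploratory work in a trial that disclaims formal testing and has no power basis. The named marker endpoint is PFS, analysed by Cox regression in the same protocol sentence, and imaging is listed by subject, so a continuous display could be added later without losing data. That stands as a limit on importance. It does not remove the gain, because the same loss of information widens an interval as well as lowering power.

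A reader might infer that response is certainly a CR-or-PR yes/no variable. The protocol does not say so; CBR or an ordered category would also fit the wording, and both shrink the loss.

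A reader might also infer that every subject has a usable percent change. Only the baseline sum is assured. The Evaluable population (Protocol 8.6.1.1) needs one dose and measurable baseline disease, not a later scan. Scans are about every 3 months or per local practice, and missing data are not imputed (SAP 7.4). Step 5 shows that dropping early failures can remove the advantage, so the ranking rule is essential.

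The simulation is also kind to the continuous measure. Real response needs confirmation and reflects non-target and new lesions. Best percent change depends on how often scans are taken, on baseline imaging that may be up to 3 months old at screening, and on permitted radiotherapy. The markers are sampled repeatedly, whereas the simulation uses one value per subject.

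**Conclusion.** The point holds as a worthwhile exploratory addition. Neither document uses the continuous change in the target-lesion sum for the marker correlatives, the response in the protocol's logistic model is undefined, and the SAP does not carry that model at all. The cost of a CR-or-PR analysis is roughly 13 to 41 points of power against Spearman under the assumptions in step 2. It is not a property of the plan: over wider inputs it is about 4 to 59 points, and under CBR near 50% or an ordinal model it is much smaller.

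A reader might go further and conclude that the trial will discard a useful selection marker or reach a wrong conclusion. The documents do not support that, because PFS by Cox regression remains the protocol's main marker analysis and no formal hypothesis test hangs on the response model.

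**What to change.** In Protocol 8.7.3 and SAP 8.4:

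- Add an exploratory Spearman correlation, with a 95% CI, of each marker with best percent change from baseline in the target-lesion sum. Because the markers are serial, name the single marker value per subject that enters it.
- Rank dosed subjects who die or progress clinically before any post-baseline scan at the worst end, tied as the largest increase. List and exclude subjects unscanned for other reasons, with a sensitivity analysis.
- State which definition of response the logistic model uses, and keep that model beside the new analysis.
- Bring SAP 8.4 into line with the protocol, including the Cox analysis of PFS as the main marker analysis.
- Leave ORR and CBR as RECIST categories.

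The cost is wording and one derived variable from data already collected. Percent change in the target sum misses progression through new or non-target lesions, which is why the categorical result is retained.
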